15.0 Alternatives

15.1 Study drug or treatment is available off-study:

Yes

No

Not applicable

15.2 * Is there a standard of care (SOC) or usual care that would be offered to prospective subjects at UCSF (or the study site) if they did not participate:

If yes, describe the SOC or usual care that patients would receive if they choose not to participate:

The standard of care would be for the patient to receive and IVC filter without randomization or physician questionnaires. The type of filter is determined by physician preference.

15.3 Describe other alternatives to study participation that are available to prospective subjects:

To not be randomized to either the Denali or Option Elite IVC filter. Also the physician would not complete a questionnaire about filter placement. In this case, the filter used is usually determined by physician choice.

16.0 Risks and Benefits

16.1 * Risks and discomforts:

Risk of IVC Filter Placement and Removal (Standard of Care)

- -Insertion site hematoma
- -Filter migration
- -Filter fracture and fragment embolization
- -Penetration of the vena cava by the filter legs
- -Recurrent PE
- -Vena cava thrombosis
- -Allergic reaction to iodinated contrast agent
- -Inability to remove IVC filter
- -Loss of privacy due to inadvertent loss of data disclosure

16.2 Steps taken to minimize risks to subjects:

Filter removal and filter placement will be conducted by a skilled M.D. Interventional Radiologist at UCSF Mission Bay, Mt. Zion, or Moffitt hospital. All MD IR staff are extensively trained in the placement and removal of IVC filters. The primary investigator will ensure the proper training of any physician placing filters on study. Patient data will be stored in APEX per standard of care or on a secured and approved UCSF database.

PI [name] MD

UCSF IRB: 14-13307	CT02201277	22 of 32
All patients included in the trial will be contacted to ur the complications associated with long-term filter dwe	. ,	
16.3 Benefits to subjects:		
• Yes • No If yes, describe: The main benefit to subjects is that they will be follow contacting them at regular intervals to ensure filter is the patient. Many IVC filter patients are not contacted for complications from the filter that also increase with	removed as soon as it is determined to be safe for for follow up retrieval and are at much greater risk	
16.4 Benefits to society:		
The benefit to society and the medical community is to of IVC filter complications and their time course. An ac standard of care for IVC filter patients and ensure the as soon as it is safe to do so.	dditional benefit is that we are trying to improve the	
16.5 Explain why the risks to subjects are reaso	nable:	
The risks to the subject are reasonable since these are having a filter placed whether or not they agreed to participate discovered during the course of the study showing the necessary in order to provide further safety data on both	articipate in the study. There may be additional risks t one device may be safer than the other. This is	

17.0 Data and Safety Monitoring Plan

17.1 Describe the plan for monitoring data and safety (Help Text updated 9/13):

DATA SAFETY MONITORING

Because this is a standard of care observational prospective study on two FDA approved and commonly used devices, our data and safety monitoring plan will primarily consist of the standard monitoring of patients during and after any clinical procedure conducted by interventional radiology.

come up during the study with either device, we will notify IRB as required and consider modifying the

ADVERSE EVENTS

study.

During the study, site personnel will note any change in the condition(s) and the occurrence and nature of any adverse events. For 30 days after removal of IVC filter, patients will be followed for any adverse event that could be related to the IVC filter or removal.

FOLLOW-UP OF PATIENTS AFTER ADVERSE EVENTS

Investigator Follow-Up:

The investigator should follow all unresolved adverse events if attributed to the IVC filter device until the event has resolved to baseline grade or better, the event is assessed as stable by the investigator, new therapy is initiated, the patient is lost to follow-up, or the patient withdraws consent. Every effort should be made to follow all serious adverse events considered to be related to trial-related procedures until a final outcome can be reported.

During the study period, resolution of adverse events (with dates) should be documented on the Adverse Event CRF and in the patient's medical record to facilitate source data verification (SDV). If, after followup, return to baseline status or stabilization cannot be established, an explanation should be recorded on the Adverse Event CRF.

DATA REVIEW

Investigators will conduct continuous review of data from UCSF enrolled patient safety at monthly research study group or site committee meetings where the results of each patient's treatment are discussed. The discussion will include the number of patients, complications as described in the protocol, and observed responses.

WITHDRAWAL

Discontinuation of Patients:

The investigator will discontinue patients from the study in the following circumstances:

- Patient is not a candidate for IVC filter retrieval to do continuing embolism risk or declining overall health status
- The patient or attending physician requests withdrawal of the patient from the study.
- The investigator stops the study or stops the patient's participation in the study for medical, safety, regulatory, or other reasons consistent with applicable laws, regulations, and good clinical practice (GCP).
- The patient is noncompliant with study procedures.

When a subject withdraws before completing the study, the reason for withdrawal is to be documented whenever known.

DSMB/DMC

A DSMB will not be utilized for the study as this is a Phase IV standard of care study on two FDA approved devices with clearly defined safety and efficacy monitoring procedures per standard clinical care. All adverse events will be reported to IRB, and other applicable regulatory agencies.

	17.2	This study	requires	a Data	and Safety	Monitoring	Board:
--	------	------------	----------	--------	------------	-------------------	---------------

Yes

No or not sure

If **yes**, press **SAVE and CONTINUE** to move to the next section of the application.

17.3 If No, provide rationale:

- C Social/Behavioral research
- O Phase I trial
- Treatment IND/Compassionate Use Trial
- Other (explain below)

If **Other**, explain:

This is a standard of care observational study of two commonly used FDA approved devices. We will discuss cases at monthly research meetings and propose changes to procedures or protocol as needed if investigators determine there are risks or adverse events directly related to the study, or if new and potentially hazardous findings are found attributable to the approved devices.

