9.0 Background

9.1 Background:

Background

The purpose of inferior vena cava (IVC) filters is preventing pulmonary embolism (PE) for patients with thromboembolic disease when standard medical therapy fails or is contraindicated (1). The most common situations for which IVC filters are used are in patients with deep vein thrombosis (DVT) or PE. Although anti-coagulation therapy is the preferred choice of prophylaxis in the setting of thromboembolic disease, many patients cannot take anticoagulants or continue to experience thromboembolism despite anticoagulation. Examples of when patients are considered for IVC filter placement include patients who have had a recent stroke, gastrointestinal bleeding, following severe trauma, and before and after surgery.

First approved for use in the late 1960's and 1970's, IVC filters were initially thought to be safe to leave in patients for life. More recent research and a flurry of lawsuits have shown that permanent placement of IVC filters can lead to a host of known and unknown side effects and complications. The society of interventional radiology (SIR) and the US Food and Drug Association now recommend retrieval of IVC filters as soon as patient's risk for embolism has subsided and when feasible and clinically indicated.

Potential complications of IVC filters include filter fracture, filter migration, and caval thrombosis (2–6). Additionally, filter components may penetrate through the wall of the IVC. This is most commonly seen with conical filters, with reported incidences varying widely by filter type (7–11). The likelihood of these complications also seems to increase over time. Therefore removal should happen as soon as clinically safe.

Use of IVC filters became commonplace after the general clinical belief in their relative safety and efficacy in preventing PE. (28–32). The advent of retrievable IVC filters has further contributed to this trend. Some filters, including the Option and Denali, are FDA approved for safety and efficacy as retrievable filters, or as permanent devices if left in place. Despite these approvals there is a relatively limited understanding of the way IVC filters behave after they are inserted (33, 34).

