The purpose of the present study is to characterize the incidence, time-course, and magnitude of complications of two commonly used IVC filters. Patients who present to Interventional Radiology for IVC filter will be randomized to have either a Denali filter or an Option filter placed. Patients will then be contacted 30-days following filter placement to come for filter removal. If it is not clinically safe for a patient to have the filter removed after 30 days, other attempts will be made to schedule for filter removal at 30-day intervals until the filter is removed. The filter placement and filter removal will be performed in the usual fashion according to the standards of our current practice. Upon filter removal, note will be made to potential complications including: filter perforation, filter migration, filter fracture and thrombus within the filter. Another main purpose of the study is to try to increase the numbers of patients who return promptly for filter removal. Many patients continue to have IVC filters in place for far longer than is needed due to poor follow up procedures and lack of tracking due to many patients being referred in from other services.

Little is presently known regarding the complication tendency of the relatively new Denali conical retrievable IVC filter (Cook, Bloomington, Indiana). The Option has been researched more and has been found to have a slightly lower incidence of complications than other conical filters.

In a prospective multicenter study of 100 Option filters, investigators noted one case of penetration among 39 filters assessed during retrieval cavograms (12); however, penetration was not dealt with as a dedicated endpoint. The option studies also did not randomize what filter was used and the data was only examined retrospectively with varying timepoints. The Denali was approved under an FDA "similar device" exemption so has not been subject to systematic long term study. The present study aims to characterize the incidence and time course of penetration and other complications at regular intervals for the Option filter compared with the Denali.

9.2 Preliminary studies:

The department of interventional radiology at UCSF has recently conducted retrospective comparative studies of IVC filter complications, comparing two devices in two separate studies. This research has inspired us to propose a randomized prospective trial to more clearly evaluate the efficacy of two newer IVC filters.

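### Section 17.1 requires discontinuation of patients who are not retrieval candidates and of noncompliant patients, without saying that contact and outcome collection continue

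*Combined protocol and SAP*

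**What the plan says.** Section 17.1, under Withdrawal, opens with mandatory wording: "The investigator will discontinue patients from the study in the following circumstances". Four circumstances follow. The first reads "Patient is not a candidate for IVC filter retrieval to do continuing embolism risk or declining overall health status" (the words after retrieval are evidently meant as due to). The last reads "The patient is noncompliant with study procedures". Noncompliance is not defined. For a subject who leaves early, the section asks only that the reason be documented where known.

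On safety follow-up, the same section states: "For 30 days after removal of IVC filter, patients will be followed for any adverse event" that could be related to the filter or its removal. It also asks for follow-up of unresolved device-attributed events, and of serious events related to trial procedures.

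Other sections describe continuing contact. Sections 7.1 and 14.1 say that a patient who is unstable or still at high clot risk is rescheduled for one month later, and that close contact is kept so that the filter comes out as soon as possible. Section 9.1 describes repeat attempts every 30 days until removal. Section 16.3 presents as the main benefit that the study follows patients by "contacting them at regular intervals to ensure filter is" removed once that is safe. Section 9.1 also says: "Another main purpose of the study is to try to increase the numbers of patients who return promptly for filter removal".

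**The concern.** The two bullets act on events after randomisation, and both concern patients who are likely still to have the filter in place. Section 9.1 says of filter complications in general: "The likelihood of these complications also seems to increase over time". A patient kept from retrieval by embolism risk or poor health, or one who misses a visit and returns later, will tend to have a longer dwell time. If study contact and data collection stop at discontinuation, later penetration, other complications and retrieval outcomes in these patients may go unrecorded. The planned survival analysis runs from insertion to the CT showing penetration, so its long-dwell end would be thinned.

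There is also a cost to the patient. Section 9.1 gives the reason for tracking: "Many patients continue to have IVC filters in place for far longer than is needed due to poor follow up procedures". A reachable patient who misses appointments is one whom the tracking is meant to help, and could be one whom the noncompliance bullet removes.

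**Working it through.** The plan gives no figure for discontinuation, so there is none to reproduce. The main check is to compare the texts.

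**1. First bullet against the follow-up plan.**
- Section 17.1: not a retrieval candidate because of continuing embolism risk or declining health → discontinue.
- Sections 7.1 and 14.1: not medically stable, or still at high clot risk → try to schedule another follow-up one month later. At the visit, a patient judged unsafe for removal is discussed with the primary care doctor, and either the filter stays permanently or later retrieval is considered.
- Section 9.1: removal not clinically safe after 30 days → further attempts at 30-day intervals until removal.

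The same clinical state leads to discontinuation in one place and to rescheduling in the others. The plan does not say which prevails.

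**2. Noncompliance bullet against the purpose.** Study procedures include the follow-up visit with rotation CT and the retrieval. No number of missed visits is set, so a missed visit could count, though the text does not say that it does. Section 9.1 makes prompt return a main purpose, and section 16.3 makes regular contact the main benefit.

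**3. What survives discontinuation.**
- Unresolved device-attributed adverse events: the listed end points include loss to follow-up and withdrawal of consent, but not discontinuation by the investigator. This follow-up may therefore continue.
- A patient with no known event: the stated 30-day window starts at filter removal. No window is given for a patient discontinued with the filter in place.
- Telephone contact, scheduling, record review and outcome data: nothing visible mentions them for a discontinued patient.

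**4. Number affected.** Section 10.4 expects half of 300 consented patients not to return: 0.5 × 300 = 150. It calls them lost to follow-up. It labels none as noncompliant or as not a retrieval candidate, so the number affected by these bullets cannot be derived from the documents.

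**5. Precision, as an illustration.** Inputs from section 8.3 are 22% and 10% penetration and 75 per group. The losses are assumptions, split evenly between arms.

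Half-width = 1.96 × √[(0.22 × 0.78 + 0.10 × 0.90)/n] = 1.96 × √(0.2616/n)

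| Lost of 150 (assumed) | n per arm | 95% half-width |
|---|---|---|
| 0 | 75 | 11.58 points |
| 2 | 74 | 11.65 points |
| 8 | 71 | 11.90 points |
| 15 | 67.5 | 12.20 points |

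At 15 lost, the ratio is √(75/67.5) = 1.054, an interval about 5% wider. The precision cost is small. This calculation says nothing about bias.

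**The case against.** The strongest reply is that this is loose withdrawal wording with little consequence. The promise of close contact in sections 7.1 and 14.1 has no exceptions, and section 16.2 (partly cut off) says that all trial patients will be contacted. CT and retrieval are standard care, the appointment is ordered at placement, and section 18.3 names all available medical records as a data source. A late returner would probably generate a CT in those records. The first bullet might also be meant only for patients finally judged unsuitable for retrieval, in which case it would not clash with monthly rescheduling.

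Much of this stands. Clinical care need not stop, and a patient who never returns lacks the study CT with or without the rule. But none of these passages says that it applies after discontinuation, and the bullet does not say that the judgement must be final. Even on that reading, it removes patients who keep the filter longest.

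A reader might infer several stronger things that the documents do not support:
- That one missed visit is noncompliance. The term is undefined.
- That the 150 expected non-returners would be discontinued under these rules. Section 10.4 calls them lost to follow-up.
- That discontinued patients are dropped from the analysis. No visible text says so.
- That the comparison of filters is biased. No reason is given for losses to differ between arms.
- That dwell-time effects are shown for these two filters. The time-dependent findings in section 9.2 concern the Gunther Tulip and Celect.

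**Conclusion.** The point holds as a gap and an internal conflict in section 17.1. Read literally, the two bullets take randomised patients out of the study with the filter in place, because of post-randomisation events, and nothing visible keeps their follow-up going. The first bullet is the stronger case, because other sections treat the same patients in the opposite way. The noncompliance bullet is weaker and depends on how an undefined term is applied.

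The concern is selective loss of longer-dwell observations and loss of study tracking, more than loss of precision. This rests on discontinuation being taken to end data collection, and on affected patients having longer dwell times, which is likely but not documented for this trial. Consent pages were not available and could contain relevant text. This is a cheap improvement to make, not evidence that the planned comparison is invalid.

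**What to change.** Add a short paragraph to section 17.1, for example:

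*A missed visit is logged as missed. Discontinuation because a patient is not a retrieval candidate, or is noncompliant, does not end follow-up. Scheduled contact, adverse-event collection, and review of medical records and any clinically obtained CT continue until 30 days after filter removal, or until the end of the study if the filter stays in. They end earlier only on loss to follow-up, withdrawal of consent, or the study being stopped. Patients are analysed as randomised, using all available data.*

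Follow-up should run to the end of the study when a filter stays in. Ending it when the filter is declared permanent would lose the patients with the longest dwell times. The paragraph covers only the two bullets at issue, so withdrawal at the request of the patient or attending physician, and the investigator's discretion to stop, are unchanged. So are the existing rule for unresolved adverse events and the treating physicians' control of retrieval timing. With this text in place, deleting the noncompliance bullet is optional.

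The cost is one paragraph, plus some extra calls and record review by the coordinator named in section 14.8, using the APEX scheduling already planned.

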18.0 Confidentiality and Privacy

18.1 Plans for maintaining privacy in the research setting:

Data are coded. A subject's protected health information (PHI) is not located on any data collection documents nor is it kept with data. Physical data are kept in locked file cabinets while electronic data are password protected and maintained on a secure network or on a password encrypted hard drive . A data key linking the subject's personal information to their study code is kept securely with access limited to staff designated by the PI.

18.2 Possible consequences to subjects resulting from a loss of privacy:

may become aware of a previously unknown medical condition. This could affect their insurability.	
18.3 Study data are:	
 □ Derived from the Integrated Data Repository (IDR) or The Health Record Data Service (THREDS) at SFGH ✔ Derived from a medical record (e.g. APeX, OnCore, etc. Identify source below) ✔ Added to the hospital or clinical medical record ✔ Created or collected as part of health care ✔ Used to make health care decisions □ Obtained from the subject, including interviews, questionnaires □ Obtained from a foreign country or countries only □ Obtained from records open to the public □ Obtained from existing research records □ None of the above If derived from a medical record, identify source: all available patient medical records (paper and electronic) 	
18.4 Identifiers may be included in research records:	
© Yes ○ No If yes, check all the identifiers that may be included: □ Names □ Dates □ Postal addresses □ Phone numbers □ Fax numbers □ Email addresses □ Social Security Numbers* □ Medical record numbers □ Health plan numbers □ Account numbers □ License or certificate numbers □ License or certificate numbers □ Vehicle ID numbers □ Device identifiers or serial numbers □ Web URLs □ IP address numbers □ Biometric identifiers □ Facial photos or other identifiable images □ Any other unique identifier * Required for studies conducted at the VAMC	
18.5 Identifiable information might be disclosed as part of study activities:	
 Yes ○ NoIf yes, indicate to whom identifiable information may be disclosed: The subject's medical record	

18.8 This study may collect information that State or Federal law requires to be reported to other officials or ethically requires action:

C Yes 🖸 No

Explain:

18.9 This study will be issued a Certificate of Confidentiality:

C Yes © No

19.0 Subjects

19.1 Check all types of subjects that may be enrolled:

▼ Inpatients

Outpatients

Healthy volunteers

☐ Staff of UCSF or affiliated institutions

19.2 Additional vulnerable populations:

Children

	NOTOGOAAGT	00 100
UCSF IRB: 14-13307 ✓ Subjects unable to consent for themselves	NCT02201277	26 of 32
✓ Subjects unable to consent for themselves (€	emergency setting)	
lacksquare Subjects with diminished capacity to consent		
Subjects unable to read, speak or understand	d English	
☐ Pregnant women ☐ Fetuses		
☐ Neonates		
☐ Prisoners		
Economically or educationally disadvantaged	persons	
☐ Investigators' staff		
☐ Students		
Explain why it is appropriate to include the type	s of subjects checked above in this particular study:	
trauma that may preclude from giving full inform provide consent. Also there are many patients w through an interpreter if necessary. Since this is	ent have experienced a medical emergency or significant ned consent. In this case, an authorized representative can ho do not speak english at UCSF who can be consented primarily an observational study, this does not place ecially true as all procedures are conducted as part of	
Describe the additional safeguards that have be of these subjects and minimize coercion or undu	en included in the study to protect the rights and welfare are influence:	
Since we are merely looking at safety data from	FDA approved devices commonly used in IVC filter	
placement as part of standard of care, patients a	are merely being asked if the data from their device used	
can be looked at. The patient or authorized repre placement as a medical necessity, the randomize	sentative will already be giving consent for filter attacks the only part of the study they must give consent	
for.		
20.0 Inclusion of Non-Engl	ich Spaaking Subjects	
^{20.0} Inclusion of Non-Engl	ish Speaking Subjects	
20.1 Indicate which method(s) you will use	e to consent non-English speaking subjects:	
consent process.	tudy documents will be available in the subject's primary ion in the patient's language will be present for the	
consent process. ✓ Short-Form—A qualified interpreter will trans	ion in the patient's language will be present for the late the consent form verbally, and subjects will be given	
consent process. ✓ Short-Form—A qualified interpreter will trans	late the consent form verbally, and subjects will be given leir primary language, following instructions in Those Who	
consent process. ✓ Short-Form—A qualified interpreter will trans the Experimental Subject's Bill of Rights in th do not Read, Speak or Understand English fo	late the consent form verbally, and subjects will be given leir primary language, following instructions in Those Who	out
consent process. ✓ Short-Form—A qualified interpreter will trans the Experimental Subject's Bill of Rights in the do not Read, Speak or Understand English for the study: 20.2 Explain how you will maintain the abilitation in the study: Use of in-person interpreter and or phone-assist care. Short-form must be used because there is	ion in the patient's language will be present for the late the consent form verbally, and subjects will be given leir primary language, following instructions in Those Who r required witnessing and signatures	put
consent process. ✓ Short-Form—A qualified interpreter will trans the Experimental Subject's Bill of Rights in the do not Read, Speak or Understand English for the stand their participation in the study: Use of in-person interpreter and or phone-assist care. Short-form must be used because there is medical team to order the placement of an IVC from same day or emergent.	ion in the patient's language will be present for the late the consent form verbally, and subjects will be given leir primary language, following instructions in Those Who r required witnessing and signatures ity to communicate with non-English speakers throughout the communicate with non-English speakers throughout interpreter will be provided, as done in standard of limited time between the decision of the patient's primary	put
consent process. ✓ Short-Form—A qualified interpreter will trans the Experimental Subject's Bill of Rights in the do not Read, Speak or Understand English for the standard English for the standa	ion in the patient's language will be present for the late the consent form verbally, and subjects will be given leir primary language, following instructions in Those Who r required witnessing and signatures ity to communicate with non-English speakers throughout the communicate with non-English speakers throughout interpreter will be provided, as done in standard of limited time between the decision of the patient's primary	put
consent process. ✓ Short-Form—A qualified interpreter will trans the Experimental Subject's Bill of Rights in the do not Read, Speak or Understand English for the stand their participation in the study: Use of in-person interpreter and or phone-assist care. Short-form must be used because there is medical team to order the placement of an IVC from same day or emergent.	ion in the patient's language will be present for the late the consent form verbally, and subjects will be given leir primary language, following instructions in Those Who r required witnessing and signatures ity to communicate with non-English speakers throughout the communicate with non-English speakers throughout interpreter will be provided, as done in standard of limited time between the decision of the patient's primary	put
consent process. Short-Form—A qualified interpreter will trans the Experimental Subject's Bill of Rights in the do not Read, Speak or Understand English for their participation in the study: Use of in-person interpreter and or phone-assist care. Short-form must be used because there is medical team to order the placement of an IVC from same day or emergent. 21.0 Recruitment 21.1 * Methods (check all that apply):	ion in the patient's language will be present for the late the consent form verbally, and subjects will be given leir primary language, following instructions in Those Who r required witnessing and signatures ity to communicate with non-English speakers throughout the communicate with non-English speakers throughout interpreter will be provided, as done in standard of limited time between the decision of the patient's primary	put
consent process. ✓ Short-Form—A qualified interpreter will trans the Experimental Subject's Bill of Rights in the do not Read, Speak or Understand English for their participation in the study: Use of in-person interpreter and or phone-assist care. Short-form must be used because there is medical team to order the placement of an IVC f same day or emergent. 21.0 Recruitment 21.1 * Methods (check all that apply): ✓ Study investigators (and/or affiliated nurses	ion in the patient's language will be present for the late the consent form verbally, and subjects will be given leir primary language, following instructions in Those Who r required witnessing and signatures ity to communicate with non-English speakers througho ed interpreter will be provided, as done in standard of limited time between the decision of the patient's primary ilter and the scheduling of the procedure which is often or staff) recruit their own patients directly in person or by	put

interested, the patient will contact the PI or the PI may directly recruit the patients (with documented

sheet for the patients.	
Study investigators provide their colleagues with a "Dear Patient" letter describing the study. This	
letter can be signed by the treating physicians and would inform the patients how to contact the study	
investigators. The study investigators may not have access to patient names and addresses for mailing	
Advertisements, notices, and/or media used to recruit subjects. Interested subjects initiate contact with study investigators. Attach ads, notices, or media text for review. In section below, please explain where ads will be posted.	
☐ Study investigators identify prospective subjects through chart review. (Study investigators request a Waiver of Authorization for recruitment purposes.)	
☐ Large-scale epidemiological studies and/or population-based studies: Prospective subjects are identified through a registry or medical records and contacted by someone other than their personal physician. (Study investigators request a Waiver of Authorization for recruitment purposes.)	
Direct contact of potential subjects who have previously given consent to be contacted for participation in research. Clinic or program develops a CHR-approved recruitment protocol that asks patients if they agree to be contacted for research (a recruitment database) or consent for future contact was documented using the consent form for another CHR-approved study.	
Study investigators list the study on the School of Medicine list of UCSF Clinical Trials website or a similarly managed site. Interested subjects initiate contact with investigators.	
 Study investigators recruit potential subjects who are unknown to them through methods such as snowball sampling, direct approach, use of social networks, and random digit dialing. Other 	
_ other	
If Other , explain:	
21.2 * How, when, and by whom eligibility will be determined:	
All patients referred for IVC filter placement procedure are initially eligible. Final eligibility will be determined by interventional radiology attending physicians who are listed on the protocol as key study personnel.	
21.3 * How, when, where and by whom potential subjects will be approached:	
21.3 * How, when, where and by whom potential subjects will be approached: Before the procedure, physicians in Interventional Radiology scheduled to do a consultation for a IVC filter placement will ask patients if they wish to participate in the observational study and consent them just as they would for the procedure consent.	
Before the procedure, physicians in Interventional Radiology scheduled to do a consultation for a IVC filter placement will ask patients if they wish to participate in the observational study and consent them just as	
Before the procedure, physicians in Interventional Radiology scheduled to do a consultation for a IVC filter placement will ask patients if they wish to participate in the observational study and consent them just as they would for the procedure consent.	
Before the procedure, physicians in Interventional Radiology scheduled to do a consultation for a IVC filter placement will ask patients if they wish to participate in the observational study and consent them just as they would for the procedure consent. 21.4 * Protected health information (PHI) will be accessed prior to obtaining consent: © Yes © No	
Before the procedure, physicians in Interventional Radiology scheduled to do a consultation for a IVC filter placement will ask patients if they wish to participate in the observational study and consent them just as they would for the procedure consent. 21.4 * Protected health information (PHI) will be accessed prior to obtaining consent:	
Before the procedure, physicians in Interventional Radiology scheduled to do a consultation for a IVC filter placement will ask patients if they wish to participate in the observational study and consent them just as they would for the procedure consent. 21.4 * Protected health information (PHI) will be accessed prior to obtaining consent: © Yes © No	
Before the procedure, physicians in Interventional Radiology scheduled to do a consultation for a IVC filter placement will ask patients if they wish to participate in the observational study and consent them just as they would for the procedure consent. 21.4 * Protected health information (PHI) will be accessed prior to obtaining consent: © Yes © No 22.0 Waiver of Consent/Authorization for Recruitment Purposes	
Before the procedure, physicians in Interventional Radiology scheduled to do a consultation for a IVC filter placement will ask patients if they wish to participate in the observational study and consent them just as they would for the procedure consent. 21.4 * Protected health information (PHI) will be accessed prior to obtaining consent: © Yes © No 22.0 Waiver of Consent/Authorization for Recruitment Purposes This section is required when study investigators (and/or affiliated	
Before the procedure, physicians in Interventional Radiology scheduled to do a consultation for a IVC filter placement will ask patients if they wish to participate in the observational study and consent them just as they would for the procedure consent. 21.4 * Protected health information (PHI) will be accessed prior to obtaining consent: © Yes © No 22.0 Waiver of Consent/Authorization for Recruitment Purposes	
Before the procedure, physicians in Interventional Radiology scheduled to do a consultation for a IVC filter placement will ask patients if they wish to participate in the observational study and consent them just as they would for the procedure consent. 21.4 * Protected health information (PHI) will be accessed prior to obtaining consent: © Yes © No 22.0 Waiver of Consent/Authorization for Recruitment Purposes This section is required when study investigators (and/or affiliated	
Before the procedure, physicians in Interventional Radiology scheduled to do a consultation for a IVC filter placement will ask patients if they wish to participate in the observational study and consent them just as they would for the procedure consent. 21.4 * Protected health information (PHI) will be accessed prior to obtaining consent: ② Yes ② No 22.0 Waiver of Consent/Authorization for Recruitment Purposes This section is required when study investigators (and/or affiliated nurses or staff) recruit their own patients directly.	
Before the procedure, physicians in Interventional Radiology scheduled to do a consultation for a IVC filter placement will ask patients if they wish to participate in the observational study and consent them just as they would for the procedure consent. 21.4 * Protected health information (PHI) will be accessed prior to obtaining consent: 22.0 Waiver of Consent/Authorization for Recruitment Purposes This section is required when study investigators (and/or affiliated nurses or staff) recruit their own patients directly. 22.1 * Study personnel need to access protected health information (PHI) during the recruitment pand it is not practicable to obtain informed consent until potential subjects have been identified.	
Before the procedure, physicians in Interventional Radiology scheduled to do a consultation for a IVC filter placement will ask patients if they wish to participate in the observational study and consent them just as they would for the procedure consent. 21.4 * Protected health information (PHI) will be accessed prior to obtaining consent: © Yes © No 22.0 Waiver of Consent/Authorization for Recruitment Purposes This section is required when study investigators (and/or affiliated nurses or staff) recruit their own patients directly. 22.1 * Study personnel need to access protected health information (PHI) during the recruitment pand it is not practicable to obtain informed consent until potential subjects have been identified.	
